2.0 TRIAL DESIGN

2.1 Trial Design

This is an open-label, single-dose study to evaluate the pharmacokinetics (PK) of intravenous (IV) MK-3866 in subjects with moderate and severe hepatic impairment (HI) compared to that of matched healthy subjects. Subjects with moderate (Panel A) and severe (Panel B) HI (classified using the Child-Pugh scale) shall be enrolled in parallel, and each Panel shall enroll a minimum of 2 subjects of each gender.

Enrollment of healthy matching control subjects (Panel C) shall commence following the completion of enrollment of either Panel A or B, whichever is completed first. Each healthy control subject will be matched to the mean body mass index (BMI; $\pm 10\%$) and age (± 15 years) of the subjects in the first HI Panel to complete enrollment. A total of 6 healthy subjects shall be enrolled into Panel C at this stage, and there should be a minimum of 2 subjects of each gender.

Following the completion of enrollment of the second HI panel, the matching characteristics (age and BMI) of the already-enrolled healthy subjects in Panel C will be compared against the mean values of the HI panel that is completed second. If any of the subjects already enrolled in Panel C do not also meet the matching criteria for the second completed HI panel, additional healthy subjects will be enrolled into Panel C in order to provide 6 healthy control

subjects who match the mean BMI ($\pm 10\%$) and age (± 15 years) of the subjects in the second HI panel. The gender of the additional healthy subject(s) will be selected to ensure that there is a minimum of 2 subjects of each gender in the group of subjects within Panel C who match with the second HI panel. On the basis of this study design Panel C may ultimately include more than 6 subjects, but no more than 12. Although enrollment efforts into Panels A and B will commence at the same time, it is expected to take longer to enroll subjects into Panel B.

The PK comparisons between each hepatically impaired Panel (A and B) and healthy controls (Panel C) will include only control subjects who meet the matching criteria for the respective HI panel.

Subjects in Panels A, B and C will receive a single IV dose of 150 mg MK-3866 (30 minute infusion, ± 5 minutes). Plasma PK assessments will be performed at pre-specified time points up to 72 hours post-dose for moderate and severe HI and up to 48 hours postdose for the healthy match control group.

[figure not shown]

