4.2 Rationale

4.2.1 Rationale for the Trial and Selected Subject Population

MK-3866 is being developed for use

[REDACTED]

[REDACTED] Gram-negative bacteria. MK-3866 has recently completed dosing the first-in-human (FIH) single ascending dose study (PN001).

The primary purpose of this study is to understand the effect of HI on the plasma PK of MK-3866 in order to guide dosing recommendations for patients with HI. As a proportion of patients with serious Gram-negative infections have baseline HI, it is important to evaluate the impact of HI on the plasma PK of MK-3866. This study will also evaluate the safety and tolerability of MK-3866 in subjects with moderate and severe HI.

Renal clearance is expected to be the major elimination pathway for MK-3866, as approximately 65% of MK-3866 is excreted in the urine following a single IV dose. Based on preclinical animal studies, hepatic elimination is anticipated to be a significant elimination pathway for MK-3866 as well and is expected to account for the remainder of the non-renal elimination of MK-3866, approximately 35%. MK-3866 is also a substrate for the liver specific transporters human organic anion transporting polypeptide (OATP) 1B1/SLCO1B1 (OATP1B1) and OATP1B3. Conducting a dedicated hepatic study for MK-3866 is in line with regulatory guidance which suggests a dedicated hepatic study be conducted for compounds in which hepatic elimination exceeds 20%.

In the FIH study of MK-3866 in healthy subjects, while single and divided doses of up to 2000 mg were generally well-tolerated, nausea was observed with an increased frequency at single doses above 800 mg. In each case, nausea was transient and its onset appeared to coincide temporally with the peak plasma concentration (although the relationship between PK and the development of nausea is currently under investigation).

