6.0 TRIAL FLOW CHART

Table 3 Trial Flow Chart – Panels A and B

Panels A and B (Subjects with HI)																					
	Screening Up to 28 days	Check-in Day -2/Day -1	Day 1															Day 2	Day 3	Day 4	Post- trial ^a
			Hours																		
			Pre-dose	0	0.5	0.75	1	1.5	2	3	4	4.5	6	8	9	10	12	24	48	72	
Administrative Procedures																					
Informed Consent	X																				
Informed Consent for Future Biomedical Research	X																				
Inclusion/Exclusion Criteria	X	X																			
Subject Identification Card	X																				
Medical History	X	X																			
Concomitant Medication Review	X-----X																		X		
Clinic Procedures/Assessments																					
Full Physical Examination	X	X																X		X	X
Child-Pugh Scale classification	X																				
Height	X																				
Weight	X																			X	
12-Lead Electrocardiogram ^b	X		X	X				X										X		X	
Vital Signs (heart rate, blood pressure)	X		X	X				X										X		X	X
Vital Signs (respiratory rate, body temperature)	X		X																		X
IV MK-3866 Administration ^c								X-----X													

Panels A and B (Subjects with HI)																					
	Screening Up to 28 days	Check-in Day -2/Day -1	Day 1															Day 2	Day 3	Day 4	Post- trial ^a
			Hours																		
			Pre-dose	0	0.5	0.75	1	1.5	2	3	4	4.5	6	8	9	10	12	24	48	72	
Adverse Events Monitoring	X-----X																				
Laboratory Procedures/Assessments																					
Laboratory Safety Tests (Hematology, Urinalysis, Chemistry)	X	X															X		X	X	
Serum β -Human Chorionic Gonadotropin (β -hCG) (females only)	X	X ^d																			
Serum Follicle Stimulating Hormone (FSH) - if applicable	X																				
Urine Drug/Alcohol/Cotinine Screen	X	X																			
HIV/Hepatitis Screen (per site SOP)	X																				
Blood for Genetic Analysis ^c			X																		
Pharmacokinetic Evaluations																					
Blood for Plasma MK-3866 Assay ^f			X		X	X	X	X	X	X		X	X	X		X	X	X	X	X	
Urine for Urinary MK-3866 Assay ^g			X	X-----X																	

Panels A and B (Subjects with HI)																				
	Screening Up to 28 days	Check-in Day -2/Day -1	Day 1														Day 2	Day 3	Day 4	Post- trial ^a
			Hours																	
			Predose	0	0.5	0.75	1	1.5	2	3	4	4.5	6	8	9	10	12	24	48	

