
PK = pharmacokinetic
 
a. All subjects who receive at least one dose of MK-3866 will return to the Clinical Research Unit (CRU) approximately 14 days after the last dose for follow-up procedures, and to determine if any adverse events have occurred since the last study visit.
 
b. Screening and predose ECGs will be performed in triplicate. At other times, single ECGs will be performed.
 
c. MK-3866 will be administered via a 30-minute IV infusion.
 
d. Women who are of non-childbearing potential (confirmed with FSH test) will not have pregnancy testing at check-in.
 
e. This sample should be drawn for planned analysis of the association between genetic variants in DNA and drug response. This sample will not be collected at the site if there is either a local law or regulation prohibiting collection, or if the IRB/IEC does not approve the collection of the sample for these purposes. If the sample is collected, leftover extracted DNA will be stored for future biomedical research if the subject signs the FBR consent. If the planned genetic analysis is not approved, but FBR is approved and consent is given, this sample will be collected for the purpose of FBR.
 
f. PK sampling scheme in plasma: Predose, 0.5 (end of infusion), 0.75, 1, 1.5, 2, 3, 4.5, 6, 8, 10, 12, 24, 48, 72 hours postdose
 
g. PK sampling scheme in urine: Predose, then pooled in the following increments: 0-4, 4-8, 8-12, 12-24 hours postdose
																				

Table 4 Trial Flow Chart – Panel C

Panel C (Healthy Control Subjects)																				
	Screening Up to 28 days	Check-in Day -2/Day -1	Day 1															Day 2	Day 3	Post- trial ^a
			Hours																	
			Predose	0	0.5	0.75	1	1.5	2	3	4	4.5	6	8	9	10	12	24	48	
Administrative Procedures																				
Informed Consent	X																			
Informed Consent for Future Biomedical Research	X																			
Inclusion/Exclusion Criteria	X	X																		
Subject Identification Card	X																			
Medical History	X	X																		
Concomitant Medication Review	X-----X																			
Clinic Procedures/Assessments																				
Full Physical Examination	X	X																X	X	
Height	X																			
Weight	X																		X	
12-Lead Electrocardiogram ^b	X		X	X				X										X		
Vital Signs (heart rate, blood pressure)	X		X	X				X				X						X	X	
Vital Signs (respiratory rate, body temperature)	X		X																X	

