7.1.5.6 Trial Procedures Modifications Permitted within Protocol Parameters

Up to additional 50 mL of blood may be drawn for safety, PK and/or PD analyses. The total blood volume withdrawn from any single subject will not exceed the maximum allowable volume during his/her participation in the entire trial (Section 12.3).

This is a Phase I assessment of MK-3866 in humans, and the PK, PD and safety profiles of the compound is still being elucidated. This protocol is written with some flexibility to accommodate the inherent dynamic nature of Phase I clinical trials.

The timing of procedures for assessment of safety procedures (e.g., vital signs, ECG, safety laboratory tests, etc.) currently outlined in the protocol may be modified during the trial based on newly available safety, tolerability, PK or PD data (e.g., to obtain data closer to the time of peak plasma concentrations). Additional laboratory safety tests may be added to blood samples previously drawn to obtain additional safety information (e.g., adding creatinine kinase to serum chemistry panel that was already drawn). These changes will not increase the number of trial procedures for a given subject during his/her participation in the entire trial.

It is understood that the current trial may employ some or none of the alterations described above. Any alteration made to this protocol to meet the trial objectives must be detailed by the Sponsor in a letter to the Trial File and forwarded to the investigator for retention. The letter may be forwarded to the IRB/ERC at the discretion of the investigator.

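### As printed, no ECG or heart rate/blood pressure reading is scheduled at the end of infusion, while the hour 0 reading largely repeats predose

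*Combined protocol and SAP*

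**What the plan says.** Section 2.1 gives every panel a "single IV dose of 150 mg MK-3866 (30 minute infusion, ± 5 minutes". Footnote f to Table 3 sets the plasma samples at "Predose, 0.5 (end of infusion), 0.75, 1, 1.5, 2, 3, 4.5, 6, 8, 10, 12, 24, 48, 72 hours postdose", so hour 0 is the start of the infusion and 0.5 h is its end. The Table 4 footnote is the same without the 72 h sample.

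In Table 3 (Panels A and B) the row "12-Lead Electrocardiogram" is marked at screening, predose, 0, 1.5, 24 and 72 h. The row "Vital Signs (heart rate, blood pressure" has the same marks plus the post-trial visit. Table 4 (Panel C) has the same early marks in both rows: predose, 0 h and 1.5 h.

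Section 7.1.5.5 allows ±30 minutes for postdose ECG and vital signs and makes the PK blood draw the critical procedure. Section 7.1.5.6 lets safety procedures be re-timed during the trial on newly available data, for example "to obtain data closer to the time of peak plasma concentrations", provided the number of procedures per subject does not rise. Adverse event monitoring is drawn as a continuous bar in both tables.

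**The concern.** Secondary objective 2 is safety and tolerability in moderate and severe hepatic impairment, and section 8.1.2.2.2 names ECGs and vital signs among the measurements that may be summarised. A concentration-related change in QTcF, heart rate or blood pressure is best looked for at the highest concentration. For a fixed infusion that moment is known in advance: it is when the infusion stops. As printed, the schedule draws blood then but takes no ECG or blood pressure. It spends one of its three Day 1 readings at a moment when no drug has yet been given and a predose reading already exists.

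Two features of the plan make this more than a matter of taste. Section 4.2.1 justifies the dose partly in terms of C_eo and says the effect of hepatic impairment is hard to predict. Section 5.1.3 also admits impaired subjects with QTcF up to 490 msec, against 450 msec for controls. If the marks are right, none of the up to 24 subjects has a scheduled ECG paired with C_eo.

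**Working it through.** **1. Column positions.** Counting cells against the headers gives:

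- Table 3, ECG (21 cells, 21 columns): screening, predose, 0, 1.5, 24, 72 h.
- Table 3, heart rate/blood pressure (21 of 21): the same, plus post-trial.
- Table 4, ECG (20 cells, 20 columns): screening, predose, 0, 1.5, 24 h.
- Table 4, heart rate/blood pressure (20 of 20): screening, predose, 0, 1.5, 4.5, 24, 48 h.

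**2. Can the positions be trusted?** Not from the cell count alone, because other rows are visibly displaced in the extracted tables:

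- The Table 3 row "IV MK-3866 Administration" also has 21 cells, yet its bar falls in the 1.5 h column. In Table 4 it falls at 0 h.
- The Table 3 safety laboratory row, again 21 cells, lands at 12, 48 and 72 h with no post-trial mark. Section 12.3 counts one post-trial collection.
- The Table 4 plasma PK row has 15 marks, one of them at hour 0. Its footnote f and section 12.3 both give 14.
- The Table 4 vital-sign rows end at 48 h with no post-trial mark.

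The Table 3 ECG and vital-sign rows have better anchors. Footnote b requires a predose ECG, and the row has one. The 24 h, 72 h and post-trial marks fall in plausible columns. Shifting the whole row one column to the right would turn predose into 0 h and push the post-trial vital-sign mark off the table. A shift of only the middle marks (0 to 0.5 h, 1.5 to 2 h) cannot be excluded from the extracted text.

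**3. Distance from the peak.** The nominal gaps to 0.5 h are 0.5 − 0 = 0.5 h after the hour 0 check and 1.5 − 0.5 = 1.0 h before the 1.5 h check. With ±30 minutes, the 1.5 h check spans 1.0 to 2.0 h. The hour 0 check spans −0.5 to 0.5 h if it counts as postdose, so it reaches the end of infusion only at the edge of its window.

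**4. Concentration at the 1.5 h check.** The inputs, from section 4.2.1 for healthy subjects, are AUC 147 µM·hr and C_eo 52 µM at 400 mg, and 272 and 97 at 800 mg. The infusion time is T = 0.5 h. In a one-compartment model, AUC/C_eo = T / (1 − exp(−kT)).

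- 400 mg: 147/52 = 2.827; 1 − exp(−0.5k) = 0.5/2.827 = 0.177; k = 0.389 per hour; half-life = 0.693/0.389 = 1.78 h.
- 800 mg: 272/97 = 2.804 gives k = 0.393 per hour; half-life 1.76 h.

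The fraction of peak remaining t hours after the infusion stops is exp(−kt). With k = 0.389:

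| Time of check | t after end of infusion | Fraction of peak |
|---|---|---|
| 1.0 h (earliest) | 0.5 h | 82% |
| 1.5 h (nominal) | 1.0 h | 68% |
| 2.0 h (latest) | 1.5 h | 56% |

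**5. Sensitivity.** If AUC rises 1.5-fold in severe impairment (section 4.2.1) through lower clearance at unchanged volume, k = 0.389/1.5 = 0.259. The nominal 1.5 h check is then at exp(−0.259) = 77% of peak. A distribution phase, which the documents do not describe, would lower all of these fractions.

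**The case against.** The strongest objection is that the finding rests on column positions in tables where other full-length rows are plainly displaced, including an hour 0 mark in Table 4 that the protocol's own text contradicts. This stands as a reason to verify the marks before acting. It does not dispose of the point, because two separate tables agree on predose, 0 and 1.5 h and the Table 3 rows are anchored by the footnote and the later columns.

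Second, the plan already offers some cover. Section 7.1.5.6 permits re-timing, section 7.1 allows unscheduled procedures, and section 7.1.2.4 allows extra vital signs. All of these are permissions; none assures a reading at the end of infusion.

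Third, the documents report no QTcF, heart-rate or blood-pressure signal and set no concentration-QT objective. ECG and vital-sign summaries are optional. This limits the weight of the point.

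Three stronger readings are tempting, and the documents do not support them:

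- A reader might infer that nothing at all is checked at the peak. Adverse event monitoring is continuous, and nausea would be captured there rather than by an ECG.
- A reader might infer that the known adverse effect occurs at the peak. Section 4.2.1 says only that "nausea was transient and its onset appeared to coincide temporally with the peak plasma concentration", adds that the relationship is still being investigated, and places the higher frequency at single doses above 800 mg. If C_eo is dose-proportional, the 150 mg peak is about 52 × 150/400 = 19.5 µM, or 19.5/97 = 20% of the 800 mg value.
- A reader might infer from the extra 4.5 h vital-sign mark in Table 4 that impaired subjects are observed less often than controls. That mark sits in a row whose right-hand end is itself doubtful, so it supports a request to reconcile the tables and no more.

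**Conclusion.** The point holds for ECG and heart rate/blood pressure only. As printed, neither flow chart schedules them at the end of infusion, and the hour 0 reading adds little to predose. The first assured postdose reading is nominally at about 68% of the peak concentration, and at about 82% to 56% across the permitted window.

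These percentages assume one-compartment kinetics and healthy-subject exposures at 400 and 800 mg; slower clearance would bring the 1.5 h reading closer to the peak. The point also assumes that the 0 h and 1.5 h marks are in their true columns, which the extracted tables do not settle. The primary PK comparisons are unaffected. It is a modest weakness in the safety objective, worth correcting because the correction is nearly free.

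**What to change.** 1. Check the 0 h and 1.5 h marks for ECG and vital signs in Tables 3 and 4 against the source tables.
2. If they stand, move the existing hour 0 ECG and heart rate/blood pressure readings, in both tables, to directly after the end-of-infusion PK draw. Keep the draw first, in line with section 7.1.5.5.
3. Give these readings their own window in section 7.1.5.5, starting no earlier than the stop of the infusion. The general ±30 minutes around 0.5 h would span 0 to 1.0 h and could put the reading back at baseline. One option is to require them before the 0.75 h PK draw; in the same model, concentration would still be at least exp(−0.389 × 0.25) = 91% of peak.
4. Reconcile the infusion row and the Day 1 vital-sign marks between Tables 3 and 4.

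The re-timing is a flow-chart edit plus one line on the window. It leaves the number of ECGs and vital-sign readings unchanged, so it also respects the limit in section 7.1.5.6. The only downside is a busier 0.5 h time point.

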7.0 TRIAL PROCEDURES

7.1 Trial Procedures

The Trial Flow Chart - Section 6.0 summarizes the trial procedures to be performed at each visit. Individual trial procedures are described in detail below. It may be necessary to perform these procedures at unscheduled time points if deemed clinically necessary by the investigator.

Furthermore, additional evaluations/testing may be deemed necessary by the investigator and or the Sponsor for reasons related to subject safety. In some cases, such evaluation/testing may be potentially sensitive in nature (e.g., HIV, hepatitis C, etc.), and thus local regulations may require that additional informed consent be obtained from the subject. In these cases, such evaluations/testing will be performed in accordance with those regulations.

7.1.1 Administrative Procedures

7.1.1.1 Informed Consent

The investigator or qualified designee must obtain documented consent from each potential subject or each subject's legally acceptable representative prior to participating in a clinical trial or Future Biomedical Research. If there are changes to the subject's status during the trial (e.g., health or age of majority requirements), the investigator or qualified designee must ensure the appropriate consent is in place.

7.1.1.1.1 General Informed Consent

Consent must be documented by the subject's dated signature or by the subject's legally acceptable representative's dated signature on a consent form along with the dated signature of the person conducting the consent discussion.

A copy of the signed and dated consent form should be given to the subject before participation in the trial.

The initial informed consent form, any subsequent revised written informed consent form and any written information provided to the subject must receive the IRB/ERC's approval/favorable opinion in advance of use. The subject or his/her legally acceptable representative should be informed in a timely manner if new information becomes available that may be relevant to the subject's willingness to continue participation in the trial. The communication of this information will be provided and documented via a revised consent form or addendum to the original consent form that captures the subject's dated signature or by the subject's legally acceptable representative's dated signature.

Specifics about a trial and the trial population will be added to the consent form template at the protocol level.

The informed consent will adhere to IRB/ERC requirements, applicable laws and regulations and Sponsor requirements.

7.1.1.1.2 Consent and Collection of Specimens for Future Biomedical Research

The investigator or qualified designee will explain the Future Biomedical Research consent to the subject, answer all of his/her questions, and obtain written informed consent before performing any procedure related to the Future Biomedical Research sub-trial. A copy of the informed consent will be given to the subject.

7.1.1.2 Inclusion/Exclusion Criteria

All inclusion and exclusion criteria will be reviewed by the investigator or qualified designee to ensure that the subject qualifies for the trial.

7.1.1.3 Subject Identification Card

All subjects will be given a Subject Identification Card identifying them as participants in a research trial. The card will contain trial site contact information (including direct telephone numbers) to be utilized in the event of an emergency. The investigator or qualified designee will provide the subject with a Subject Identification Card immediately after the subject provides written informed consent. At the time of treatment allocation/randomization, site personnel will add the treatment/randomization number to the Subject Identification Card.

7.1.1.4 Medical History

A medical history will be obtained by the investigator or qualified designee.

7.1.1.5 Prior and Concomitant Medications Review

7.1.1.5.1 Prior Medications

The investigator or qualified designee will review prior medication use, including any protocol-specified washout requirement, and record prior medication taken by the subject within 14 days before the first dose of trial medication.

7.1.1.5.2 Concomitant Medications

The investigator or qualified designee will record medication, if any, taken by the subject during the trial.

7.1.1.6 Assignment of Screening Number

All consented subjects will be given a unique screening number that will be used to identify the subject for all procedures that occur prior to randomization or treatment allocation. Each subject will be assigned only one screening number. Screening numbers must not be re-used for different subjects.

Any subject who is screened multiple times will retain the original screening number assigned at the initial screening visit.

Specific details on the screening visit requirements (screening/rescreening) are provided in Section [7.1.5.1](#).

